Historical pooled PFS6 is approximately 20% for previously used agents. In this study, those progressing within 6 months of prior therapy will be enrolled with the goal of detecting PFS6 in $\geq 20\%$ of patients, while PFS6 in <5% will be considered to be of poor interest. Selecting patients following 1-3 prior regimens and within 6 months of prior therapy will ensure timely accrual of a homogeneous population and enrich for patients unlikely to attain PFS6 without active therapy. Thus, outcome results will be more interpretable, given these stipulations. Tumor tissue will be collected to be studied retrospectively to analyze genomics/proteomics to identify an association with PFS6.

Nanostring platform for gene expression analysis of formalin-fixed paraffin embedded tumor

Gene expressing profiling performed by the nanostring technology, which utilizes formalin-fixed paraffin embedded (FFPE) tissue using the nCounter® appears highly promising (59). This technology provides robust data from FFPE tissue using the nCounter® GX Kit and offers high levels of precision and sensitivity (>1 copy per cell) without the need for amplification of ≥ 100 ng of RNA. Nanostring is a multiplexed (up to 800 genes per reaction) platform, which utilizes digital counting and excellent quantitative reproducibility by employing two ~50 base probes per mRNA that hybridize in solution. Multiple successful applications utilizing the nCounter System to subtype tumors, formulate tumor prognostic signatures, or discover novel targets for therapy have been reported in other malignancies (60-63). Notably, the 50-gene PAM50 signature (Prosigna™) derived from nanostring was approved by the US FDA in 2013 to assess the risk of distant recurrence at 10 years in postmenopausal women with hormone receptor-positive breast cancer. Indeed, the PAM50 gene score, which is enriched for proliferation-associated genes appeared more robust than the Oncotype DX® recurrence score in predicting recurrence (62). Gene expression by nanostring may be proposed for a highly relevant panel of 797 genes including 230 human cancer-promoting genes, 519 kinase genes, 32 bladder cancer specific genes recently reported by TCGA including 4 genes involved in epigenetic regulation, 85 DNA damage repair genes, 3 stem cell relevant genes and 8 internal reference genes (64).

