2.3 Exploratory objectives

- Association of tumor IHC for Tie2 and VEGFR2 with PFS
- Association of Gene expression in tumor tissue using Nanostring technology

3. Investigator[s] and other study participants

Principal Investigator

[name]
UAB Comprehensive Cancer Center
[name]
[name]
[contact]
[contact]
Email address: [contact]

Co-Investigators

[name]
[name]
[name]

[name], MD is a Professor in Department of Medicine, division of Hematology and Oncology at University of Alabama at Birmingham (UAB) and a Scientist at UAB Comprehensive Cancer Center (UABCCC). [name] is the director of urologic oncology at Wayne State University Karmanos Cancer Institute, and has extensively accrued in urothelial cancer trials and published multiple studies. [name], MD is an

[figure not shown]
Assistant Professor in the Department of Medicine, Division of Hematology and Oncology at UAB. He will see patients at Kirklin clinic along with [name]. [name] is a faculty urologic medical oncology physician with Cleveland Clinic where he is active with clinical trials and patient care.

4. Study design

This is a 3-center one-stage phase II trial conducted at the UAB Comprehensive Cancer Center (Birmingham, AL), Wayne State Karmanos Cancer Institute (Detroit, MI), and the Cleveland Clinic (Cleveland, OH). The trial will be managed by the Clinical Trial Network Monitoring Office (CTNMO) housed at the UAB Comprehensive Cancer Center. Progression free survival at 6 months is the primary end- point and the trial will enroll 35 patients. The eligible population includes patients with advanced urothelial cell carcinoma who have progressive disease after 1-3 prior chemotherapy regimens. Regorafenib is taken orally and is administered daily for the first 21 days of each 28 day cycle. The dose of Regorafenib is 120 mg once daily for the first cycle, which will be escalated to 160 mg once daily from the second cycle if no Regorafenib-related toxicities greater than grade 1 occur. Each 28 day cycle will be repeated until disease progression, intolerable toxicities, or patient decision with no limit on number of cycles allowed. Radiological evaluations are performed at each institution using RECIST 1.1 criteria every 2 cycles (8 weeks) or earlier if clinically indicated. Progression free-survival will be defined as the time to first occurrence of any of the following:

1. Clinical symptoms and signs of progression of disease,

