7.2 Efficacy

7.2.1 End points of efficacy

The primary endpoint of the study is to evaluate progression free survival (PFS) at 6 months (PFS6). Secondary endpoints of this study are evaluating measurable disease response rate using RECIST 1.1 criteria, measuring survival and toxicities after receiving Regorafenib.

Immunohistochemistry and gene expression using Nanostring technology for a panel of kinase and cancer associated genes to correlate with tumor response may be performed and are potential endpoints based on outcomes.

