7.2.2 Exploratory tumor tissue studies and central pathology review

Twenty archival formalin-fixed paraffin-embedded (FFPE) tumor slides will be requested for potential central pathology review and molecular studies. Fifteen slides of 10 μM thickness sections each and 5 slides of 5 μM thickness sections each will be requested from all institutions. In the event of attainment of the primary endpoint (i.e. PFS6 in $\geq 20\%$ of patients), slides will be obtained and following central pathology review for determining histologic subtype, tumor will be demarcated from adjacent normal tissue on the H+E slide to guide procurement of tumor-enriched samples. The 10 μM sections will be used for RNA isolation toward gene expression profiling for ~ 800 cancer-promoting, kinase, DNA-damage repair, bladder cancer-specific and stem cell panel genes by the nanostring platform performed centrally in the UAB Comprehensive Cancer Center. A total surface area of tumor 100 mm^2 is adequate to harvest the necessary amount of RNA (100 ng) using the RNAeasy Mini Kit (Qiagen), and the quality of the RNA will be assessed via the 260/280 ratio using nanodrop. [name] at UAB Radiation Oncology Dept. will perform the nanostring studies as described in previous publications utilizing the nCounter by inputting RNA directly into a hybridization reaction containing color-coded molecular barcodes representing the genes of interest [56]. Immunohistochemistry (IHC) is performed on the 5 μM section slides for VEGFR2 and Tie2 by previously described methods using appropriate controls.

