Although a clear progression of "non-target" lesions only is exceptional, the opinion of the treating physician should prevail in such circumstances, and the progression status should be confirmed at a later time by the review panel (or Principal Investigator).

Evaluation of Best Overall Response

The best overall response is the best response recorded from the start of the treatment until disease progression/recurrence (taking as reference for progressive disease the smallest measurements recorded since the treatment started). The patient's best response assignment will depend on the achievement of both measurement and confirmation criteria.

Target Lesions	Non-Target Lesions	New Lesions	Overall Response	Best Response for this Category Also Requires:
CR	CR	No	CR	≥ 4 wks. confirmation
CR	Non-CR/Non-PD	No	PR	≥ 4 wks. confirmation
PR	Non-PD	No		
SD	Non-PD	No	SD	documented at least once ≥ 4 wks. from baseline
PD	Any	Yes or No	PD	no prior SD, PR or CR
Any	PD*	Yes or No	PD	
Any	Any	Yes	PD	

* In exceptional circumstances, unequivocal progression in non-target lesions may be accepted as disease progression.

Note: Patients with a global deterioration of health status requiring discontinuation of treatment without objective evidence of disease progression at that time should be reported as "symptomatic deterioration". Every effort should be made to document the

objective progression even after discontinuation of treatment.

Duration of Response

The duration of overall response is measured from the time measurement criteria are met for CR or PR (whichever is first recorded) until the first date that recurrent or progressive disease is objectively documented (taking as reference for progressive disease the smallest measurements recorded since the treatment started).

The duration of overall CR is measured from the time measurement criteria are first met for CR until the first date that recurrent disease is objectively documented.

Duration of stable disease: Stable disease is measured from the start of the treatment until the criteria for progression are met, taking as reference the smallest measurements recorded since the treatment started.

Progression-Free Survival

PFS is defined as the duration of time from start of treatment to time of progression or death, whichever comes first.

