8.3 Statistical and analytical plans

The primary endpoint of the study is the rate of progression free survival (PFS) at 6 months (PFS6). Given the poor prognosis of this patient population and data from other studies of salvage therapy, a PFS6 of $\geq 20\%$ is felt to be important for this regimen, while a PFS6 $< 5\%$ is felt to be of poor interest. The trial also enrolls patients who progress within 6 months of last cycle of prior chemotherapy to enhance the interpretability of outcomes, since such patients are unlikely biologically to be progression-free for 6 more months without active therapy that favorably impacts on tumor biology to extend PFS. SAS version 9.3 was used to calculate power. The justification for the proposed sample size is based on an exact test for a binomial proportion with a one-sided significance level of 5%. With 32 evaluable subjects,

we will have approximately 80% power (79.6%) to reject the null hypothesis that PFS6 is < 5% in favor of PFS6 \geq 20%. Given that 5-10% of patients may be inevaluable, up to 35 patients may be enrolled. If five or more patients remain progression-free at 6 months, this regimen will be considered to be of significant interest.

Chi-square or Fisher's exact test will be employed to determine univariate association of biomarker status with PFS6 and objective response. Descriptive statistics including frequencies and proportions will be calculated to summarize safety and toxicity outcomes. Specifically, the number of adverse events (AE) and serious adverse events (SAE) will be tabulated and summarized. Point estimates and exact binomial (Clopper-Pearson) confidence intervals (CI) will be calculated to estimate the incidence of AEs and SAEs. The precision of these estimates, i.e., width of the confidence interval, will depend on the estimated incidence of each outcome. The table below gives the exact 95% confidence intervals for a range of incidences, assuming 32 evaluable subjects.

Number of subjects experiencing event	Estimated Incidence	95% Exact CI for Incidence		Width of CI
		Lower Limit	Upper Limit	
1	0.031	0.001	0.162	0.161
2	0.062	0.008	0.208	0.200
4	0.125	0.035	0.290	0.255
8	0.250	0.115	0.434	0.319
16	0.500	0.319	0.681	0.362

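### The exploratory IHC objective names PFS, but markers are tested only against binary PFS6 and response, so that objective has no matching analysis

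*Combined protocol and SAP*

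**What the plan says.** The outcome for the tissue markers is worded differently in each place it appears.

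- Section 2.3, IHC objective: "Association of tumor IHC for Tie2 and VEGFR2 with PFS".
- Section 2.3, gene-expression objective: "Association of Gene expression in tumor tissue using Nanostring technology", with no outcome named.
- Section 1.2: tissue is collected "to analyze genomics/proteomics to identify an association with PFS6".
- Section 7.2.1: IHC and Nanostring expression "to correlate with tumor response may be performed and are potential endpoints based on outcomes".
- Section 8.3, and the synopsis in the same terms: a chi-square or Fisher's "exact test will be employed to determine univariate association of biomarker status with PFS6 and objective response".

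Section 7.2.2 makes the slide work conditional: "In the event of attainment of the primary endpoint", which it glosses as PFS6 in at least 20% of patients. Section 7.2.3 defines PFS as a time: "PFS is defined as the duration of time from start of treatment to time of progression or death, whichever comes first". Imaging runs every 8 weeks until progression (section 7.1, note A). No log-rank, Cox or other time-to-event analysis by marker appears anywhere. The documents give no marker prevalence, effect size, alpha or power for the marker tests, and no rule for choosing between chi-square and Fisher.

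**The concern.** If section 8.3 is followed as written, the IHC objective in section 2.3 is never analyzed. What is analyzed is a dichotomized version of PFS, plus response. A patient who progresses at 1 month and one who progresses at 5.5 months count as the same failure, although the protocol already defines and measures the time. With few patients expected to be progression-free at 6 months, a two-by-two test has little to work with, so a real association with Tie2 or VEGFR2 is easier to miss than it need be. With three outcomes named in different sections, the choice of outcome could also be made after the data are seen.

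**Working it through.** **The plan's own figure.** Section 8.3 tests 5% against 20% with 32 evaluable patients and calls the regimen of interest at 5 or more successes. Exact binomial: P(X ≥ 5 | 32, 0.20) = 0.7956, matching the stated 79.6%; P(X ≥ 5 | 32, 0.05) = 0.0204. The design figure reproduces. No power is stated for the marker tests.

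**Information discarded.** At PFS6 = 20%, expected failures by 6 months are 0.80 × 32 = 25.6, about 26. Expected successes are 6.4, or 3.2 per group in an even split. That is below the usual minimum expected count of 5 for chi-square.

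**Assumptions, because the documents give none.** Exponential PFS; overall PFS6 20%; n = 32; 12 months of follow-up; two-sided 5%; hazard ratio (HR) 0.5 in favor of the favorable marker group; favorable share 25% to 75%. The only related shares in the documents are for the ligands Ang-1 (35%) and Ang-2 (44%) in section 1.1.2, not for Tie2 or VEGFR2.

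**Method.** With favorable fraction w, solve w·s^HR + (1 − w)·s = 0.20 for s, the PFS6 in the unfavorable group. For w = 0.5 and HR 0.5, s = 0.094 and the favorable group has √0.094 = 0.306; their mean is 0.200. Fisher and uncorrected chi-square power come from exact enumeration of both binomials. Log-rank power is simulated (20,000 runs).

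| Favorable / other | PFS6 favorable / other | Fisher | Chi-square | Log-rank |
|---|---|---|---|---|
| 8 / 24 | 0.376 / 0.141 | 27% | 34% | 34% |
| 11 / 21 | 0.349 / 0.122 | 29% | 32% | 41% |
| 16 / 16 | 0.306 / 0.094 | 19% | 34% | 46% |
| 21 / 11 | 0.267 / 0.071 | 9% | 24% | 45% |
| 24 / 8 | 0.246 / 0.061 | 3% | 7% | 40% |

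Repeat simulations move the log-rank entries by a point or two (46% to 48% at 16/16). At HR 0.4 and 16/16 the powers are 34%, 52% and 69%. Over HR 0.33 to 0.6 and shares of 25% to 75%, the ratio to log-rank power runs from 0.07 to 0.82 for Fisher and from 0.17 to 1.08 for chi-square.

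**Cross-check of log-rank at 16/16.** The hazards are 0.197 and 0.394 per month, so expected events by 12 months are 32 × [1 − (0.094 + 0.009)/2] = 30.4. The Schoenfeld formula gives Φ(0.693 × √(30.4 × 0.25) − 1.96) = Φ(−0.05) = 48%.

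**Sensitivity.** In 3,000-run checks at 16/16 and HR 0.5, dating progression on the 8-week scans gives 46%, and stopping follow-up at 6 months gives 43%, against 48% in the base run of the same size.

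**Test size.** With no association, 16/16 and PFS6 20%, actual size is 1.8% for Fisher, 5.3% for chi-square and about 6% for the asymptotic log-rank. The tests are therefore not size-matched. Part of Fisher's shortfall is conservatism, and the log-rank figures are slightly flattering.

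**Granularity of Fisher at 16/16.** With 5 successes, a 5–0 split gives p = 2 × C(16,5)/C(32,5) = 2 × 4368/201376 = 0.043, and 4–1 gives p = 0.33. With 7 successes, 7–0 gives 2 × 11440/3365856 = 0.007, and 6–1 gives 2 × (11440 + 16 × 8008)/3365856 = 0.083. In both cases Fisher rejects only when every success lies in one group.

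**The case against.** The strongest reply is that PFS6 is deliberate. Section 1.1.1 argues for it as the endpoint best linked to survival, and section 1.2, the synopsis and section 8.3 all name it for the markers. Only one of the two bullets in section 2.3 says PFS. Changing that word to PFS6 would bring it into line with those three places. This stands as far as it goes: the mismatch is confined to the IHC bullet, and a reader should not infer that PFS is the stated outcome for all the tissue work. But PFS is what the objective says, and the data for it are collected anyway.

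A reader might also infer that the planned tests roughly halve the power. The documents do not support a fixed figure. A halving fits Fisher near an even split. Chi-square, which section 8.3 also allows, loses about a quarter there (34% against 46%) and nothing at 8/24, while both tests lose far more when most patients are in the favorable group.

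The 5-success illustration has a limit too. Under section 7.2.2 the trigger is at least 20%, which needs 7 of 32 (6/32 = 18.8%), so a trial with 5 successes (15.6%) would not reach the marker tests under that wording. It would under the section 8.3 rule of 5 or more.

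Finally, log-rank power is itself below 50% at HR 0.5, the work is optional and affects no decision, and scans after stopping without progression are recorded only if available. All of that stands and lowers the priority. The last point affects PFS6 equally, since patients not followed to 6 months have no clear binary status, whereas a time-to-event analysis can censor them.

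**Conclusion.** The point holds as a mismatch between objective and analysis. The IHC objective in section 2.3 is PFS, nothing in section 8.3 or the synopsis analyzes PFS by marker, and sections 1.2 and 7.2.1 name other outcomes. This part rests on the text alone.

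That a time-to-event test would usually have more power rests on the assumptions stated (exponential PFS, proportional hazards, overall PFS6 20%, n = 32). The gain ranges from none (chi-square, 8/24) to large (either test with most patients favorable). It cannot be given as one number until the split and the test are known, and part of the gap to Fisher reflects unequal test size. The objective is exploratory and conditional on meeting the primary endpoint, so this is a cheap improvement of low priority. It does not affect the primary conclusion.

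**What to change.** In section 8.3, add a log-rank or Cox analysis of PFS time by Tie2 and VEGFR2 IHC status, with permutation p-values because the asymptotic log-rank is slightly liberal at this size. Name it as the analysis of the IHC objective in section 2.3. Keep the chi-square or Fisher tests of PFS6 and objective response as supporting analyses. Make sections 1.2, 2.3, 7.2.1 and 8.3 name the same outcomes, including one for the gene-expression bullet, which now has none.

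The cost is wording only; no patients, visits or scans are added. The downside is one more exploratory analysis, which at HR 0.5 would still have less than about 50% power. It should be reported as hypothesis-generating, with estimates and confidence intervals.

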9.1 Data recording

The trial protocol will undergo initial review by the Clinical Trials Review Committee (CTRC) and IRB (Institutional Review Board) of the central coordinating site, UAB Comprehensive Cancer Center. Thereafter, the scientific review committee of each institution will review the protocol followed by IRB approval for each institution. The registration of patients will be conducted as per described in section 5.1.4. The data manager at each institution enters data on the electronic case report forms (eCRFs) directly. Patient eligibility is verified based on the entries in the eCRF. The Clinical Trials Network (CTN) of the UAB Comprehensive Cancer Center (CCC) coordinates investigator-initiated clinical trials under Good Clinical Practice conditions at CTN affiliate sites of UAB and other participating institutions. The CTN Monitoring Office (CTNMO) will maintain shadow charts for the patients entered on trial. The data entered into the eCRFs for each protocol specific time point will be compared to the source for accuracy and completeness. Queries will be generated as needed. All patients for this trial will be registered into the OnCore system for study patient tracking for this trial for the UAB Comprehensive Cancer Center.

9.2 Monitoring

This protocol will adhere to the policies and requirements of the NCI CTEP Multicenter Guidelines. The specific responsibilities of the Principal Investigator and the UAB study coordinator and the procedures for auditing are presented in section 9.4. The Principal Investigator and CTNMO are responsible for distributing all Safety Reports to all coordinating centers for submission to their individual IRBs for action as required.

Each study subject is discussed at the CTN site's monthly Clinical Trials Monitoring Committee meeting by the CTN site research nurses and participating site Lead Investigators and is, in turn, presented at the next monthly Clinical Trials Monitoring Committee meeting by the CTNMO Manager. The P.I. (assisted by the CTNMO Manager) is the primary contact for study-specific questions such as dose modifications, toxicities, and supportive care. The CTNMO Manager is the primary contact for issues regarding patient registration, regulatory documentation, completion of eCRFs, data collection, and data submission electronically. Comprehensive monitoring of studies (100% of patients) is conducted using the electronic data CRFs and supporting source documents that are transmitted to the Department of Biostatistics. Following each monitoring exercise, queries and/or requests for additional documentation are generated by the CTNMO Manager generally within 2 weeks of receipt of the CTN affiliate site and participating site documents. Subsequently, the CTN affiliate site and participating sites review and respond to queries and implements the necessary corrective action(s). Within two weeks, the CTN affiliate site and participating site submits query responses and, if appropriate, a written summary of corrective actions to the CTN Coordinating Center Manager. The CTN Coordinating Center Manager conducts "on-site" monitoring visits at least once a year to verify data from source charts and to provide staff education and to assist in implementing corrective action.

9.3 Data processing

After completion of the study, i.e. when the study has been concluded in accordance with this protocol and the last patient completed his/her last follow-up visit (last patient out), an integrated clinical and statistical study report containing a complete and detailed analysis and summary of all observations, results and conclusions related to or resulting from the study shall be written by the sponsor in consultation with the Principal investigator within twelve (12) months after completion of the study.

The study report shall be compiled in accordance with the ICH-E3 Guideline.

